9.5. Distribution and Shipment

Export and import of IMPs will be carried out according to the provisions of Directive 2001/20/EC, Article 13.

Distribution and shipment of IMPs will be performed by a sub-contracted distribution CRO in appropriate shippers to maintain the required storage conditions of the study drugs. For the laquinimod capsules, bottles will be packed and shipped at room temperature in appropriate storage boxes.

Each shipment of IMPs supplies for the study will contain a shipment form describing the contact of shipment. This form will assist in maintaining current and accurate inventory records. When a shipment is received, the Investigator/Coordinator/pharmacist will acknowledge receipt of the IMPs supply by making 'Shipment Activation Call' (via the IVRS) and by signing on the shipment form and faxing it back to the distribution center (where applicable). For the open-label phase (LAQ/5063 OL) IVRS will not be used. Laquinimod 0.6 mg daily dose will be available at the sites.

If, upon arrival at the investigational site, the IMPs supplies appear to be damaged, the CSU should be contacted immediately.

9.6. Storage, Dispensing and Return

IMP supplies must be kept in a secure, limited-access, refrigerated (2° -8°C) and controlled storage area.

Only authorized personnel will have access to the IMP supplies.

The study site personnel at each site will be responsible for correct storage and handling of the study products. The IMPs supplies will be stored safely and properly in a temperature-controlled refrigerator (2°- 8°C), and must be kept under the prescribed conditions. The subjects should be instructed to store the IMPs (in their original package) in a refrigerator.

The IMP pack/s will be dispensed to the subject at the study site at each study visit starting at baseline visit (except for termination visit). The subjects will be instructed to administrate the study drugs once daily at approximately the same time of the day. The packs will be assigned to subjects by using an IVRS (this is relevant for LAQ/5063 active double-blind phase only). After assigning a pack number to the subject, the Investigator/Pharmacist/Coordinator should fill in manually the subject's number and investigator's name on the label of the dispensed monthly

pack, as well as on the detachable parts, which will be attached to the source document and prescription form (where applicable).

Subjects will be instructed to return all the empty blisters and unused study drugs in their original packs.

Upon approval of the Amendment #4 to LAQ/5063 the process will be changed to the following:

The IMP supplies which will be supplied in bottles must be stored at room temperature (15-25°C) in a limited access secured storage area.

The IMP bottles will be dispensed to the subject at the study site at each study visit following the approval of this amendment and the supply process which will follow the approval. The bottles will be assigned to subjects by the site personnel. After assigning a bottle number to the subject, the site personnel should fill in the subject's number, the visit number and the dispensing Investigator's name on the label of the dispensed bottle as well as on the detachable parts that would be attached to the subject's file.

At each visit the subject will receive the amount of bottles of IMP according to visit interval, an amount that will suffice until the following scheduled dispensing visit.

Subjects will be instructed to return all used empty bottles and unused IMP at each visit. The Site Investigator/site coordinator is responsible for performing IMP accountability at the site. The Monitor is responsible for the accountability of the returned IMPs.

9.7. Route And Dosage Form

The following will be administered for each treatment group **during the double blind phase**:

- 0.3 mg group one white to off-white round biconvex tablet of 0.3 mg of laquinimod and one matching placebo tablet to be administered orally once daily.
- 0.6 mg group: two white to off-white round biconvex tablets of 0.3 mg of laquinimod tablets to be administered orally once daily.

For the open label phase (LAQ/5063 OL) all subjects will receive 0.6 mg of laquinimod: two white to off-white round biconvex tablets each of 0.3 mg of laquinimod to be administered orally once daily. Upon approval of Amendment # 4 for (LAQ/5063 OL) all subjects will be administered one capsule of laquinimod 0.6 mg to be taken orally at the same hour every day.

Capsules should be swallowed with a glass of water.

9.8. Verification of Compliance With Treatment Regimen

The subject will be requested to return all IMPs unused tablets/capsules (upon the switch to capsules following Amendment # 4 to LAQ/5063 protocol) in the original *packages (blisters or bottles)* to the study site at every visit.

Compliance with the dosing regimen will be determined by performing accountability of returned IMPs. The number of returned tablets (**until the switch** to capsules will occur)/capsules will be counted and recorded in the CRF by site personnel.

The subject number, pack number, batch code number, quantity of IMPs returned by the subject and visit date will be recorded by the site personnel. After the switch to the capsule formulation, batch number will be allocated instead of a batch code number.

The IMPs accountability records must be maintained at the site at all times.

Compliance will be calculated as a percentage by calculating the number of used capsules/tablets (tablets compliance will be calculated until the last tablets will be returned) divided by the number of total capsules/tablets(tablets compliance will be calculated until the last tablets will be returned) multiplied by 100.

Subjects with less than 75% overall compliance during the entire study will be considered non-compliant (see Section 8.3).

9.9. Accountability

Upon Teva's (or Teva's designee) monitor visit at the site, accountability of the returned IMPs should be performed and recorded by the monitor. The subject number, pack number, batch code number, quantity of IMPs returned by the subject and the date of accountability should be recorded on the appropriate accountability forms, to be provided by the CSU.

The IMPs accountability records must be maintained at the site at all times.

After accountability of returned study drugs is performed and recorded, all IMPs unused tablets (all tablets should be returned upon the switch to capsules) /capsules must be returned by the monitor to the Sponsor or Sponsor's designee for destruction.

Accountability forms, filled in by the Study Monitor, must be sent with the returned IMPs for verification and a copy is left at the site in the Investigator's file.

10. SAFETY AND PHARMACOVIGILANCE

Adverse Event

An AE is defined as any untoward medical occurrence in a clinical trial subject administered a medicinal product and which does not necessarily have a causal relationship with the treatment.

In the study, any event occurring after the clinical trial subject has signed the study Informed Consent should be recorded and reported as an AE.

An AE can therefore be any unfavorable and unintended sign (including an abnormal laboratory finding), symptom, or disease temporally associated with the use of an IMP, whether or not considered related to the IMP.

A new condition or the worsening of a pre-existing condition will be considered an AE. Stable chronic conditions such as arthritis that is present prior to study entry and do not worsen during the study will not be considered AEs.

Worsening of the disease under study will be measured by evaluation of conditions suggestive of MS relapse or by EDSS parameters, and should only be recorded as an AE if the outcome is more serious than would normally be expected from the normal course of the disease in a particular subject.

An abnormal result of diagnostic procedures including abnormal laboratory findings will be considered an AE if it:

- Results in subject's withdrawal by the investigator
- Is associated with a SAE
- Is associated with clinical signs or symptoms
- Is considered by the physician to be of clinical significance

The intensity or severity of the AE will be characterized as:

- Mild: AE which is easily tolerated
- Moderate: AE sufficiently discomforting to interfere with daily activity.
- Severe: AE which prevents normal daily activities.

Unlabeled/ Unexpected AE - A reaction which is not included in the Adverse Reaction section of the relevant Reference Safety Information by its specificity, severity, outcome or frequency. The labeling reference of this study is the IB.

The relationship to study treatment is characterized as in the below table until Month 60, inclusive:

TERM	DEFINITION	CLARIFICATION
Unrelated	This category applies to those AEs which, after careful consideration, are clearly and incontrovertibly due to extraneous causes (disease, environment, etc.)	
Unlikely	In general, this category can be considered applicable to those AEs, which, after careful medical consideration at the time they are evaluated, are judged to be unrelated to the IMP.	An AE may be considered unlikely related if or when at least 2 of the following apply: 
 • It does not follow a reasonable temporal sequence from the administration of the IMP. • It could readily have been produced by the subject's clinical state, environmental or toxic factors, or other modes of therapy administered to the subject. • It does not follow a known pattern of response to the IMP. • It does not reappear or worsen when the IMP is re-administered.
Possibly	This category applies to those AEs for which, after careful medical consideration at the time they are evaluated, a connection with the IMP administration appears unlikely but cannot be ruled out with certainty.	An AE may be considered possibly related if or when at least 2 of the following apply: 
 • It follows a reasonable temporal sequence from administration of the IMP. • It could not readily have been produced by the subject's clinical state, environmental or toxic factors, or other modes of therapy administered to the subject. • It follows a known pattern of response to the IMP.
Probably	This category applies to those AEs which, after careful medical consideration at the time they are evaluated, are felt with a high degree of certainty to be related to the IMP.	An AE may be considered probably related if or when at least 3 of the following apply: 
 • It follows a reasonable temporal sequence from administration of the IMP. • It could not be reasonably explained by the known characteristics of the subject's clinical state, environmental or toxic factors or other modes of therapy administered to the subject. • It disappears or decreases on cessation or reduction in dose. There are important exceptions when an AE does not disappear upon discontinuation of the IMP, yet IMP-relatedness clearly exists. • It follows a known pattern of response to the IMP.

The relationship to study treatment from Month 60 and thereafter is characterized as in the below table:

TERM	DEFINITION	CLARIFICATION
No Reasonable Possibility	This category applies to those adverse events which, after careful consideration, are clearly due to extraneous causes (disease, environment, etc.) or to those adverse events, which after careful medical consideration at the time they are evaluated, are judged to be unrelated to the test drug.	An adverse event may be considered No Reasonable Possibility if it is clearly due to extraneous causes or when (must have two): 
 • It does not follow a reasonable temporal sequence from the administration of the test drug. • It could readily have been produced by the subject's clinical state, environmental or toxic factors, or other modes of therapy administered to the subject. • It does not follow a known pattern of response to the test drug. • It does not reappear or worsen when the drug is re-administered.
Reasonable Possibility	This category applies to those adverse events for which, after careful medical consideration at the time they are evaluated, a connection with the test drug administration cannot be ruled out with certainty or felt with a high degree of certainty to be related to the test drug.	An adverse event may be considered Reasonable Possibility related if or when (at least two of the following): 
 • It follows a reasonable temporal sequence from administration of the drug. • It could not be reasonably explained by the known characteristics of the subject's clinical state, environmental or toxic factors, or other modes of therapy administered to the subject. • It disappears or decreases on cessation or reduction in dose. There are important exceptions when an adverse event does not disappear upon discontinuation of the drug, yet drug-relatedness clearly exists. • It follows a known pattern of response to the test drug.

The date of onset, a description of the AE, severity, seriousness, action taken, relationship to the study drug, outcome of the event and date of resolution will be recorded.

Serious Adverse Event

A SAE is defined as an AE that results in any of the following:

- death
- life-threatening
- requires hospitalization or prolongs existing inpatients' hospitalization

- results in persistent or significant disability or incapacity
- results in a congenital abnormality or birth defect
- an important medical event which requires medical intervention to prevent any of the above outcomes.

Important medical events are those which may not be immediately life-threatening, but may jeopardize the subject and may require intervention to prevent one of the other serious outcomes listed above. Examples of such events are intensive treatment in an emergency room or at home for allergic bronchospasm; blood dyscrasias or convulsions that do not result in hospitalization; resulting in an AE will normally be considered serious by this criterion.

Inpatient **hospitalization** or prolongation of existing hospitalization means that hospital inpatient admission and/or prolongation of hospital stay were required for treatment of AE, or that they occurred as a consequence of the event. It does not refer to pre-planned elective hospital admission for treatment of a pre-existing condition that has not significantly worsened, or to diagnostic procedure. It does not refer either to hospitalization for iv steroid treatment of a relapse, unless it is a worsening of condition beyond expected disease progression.

The term "**life-threatening**" in the definition of "serious" refers to an event in which the subject was at risk of death at the time of the event; it does not refer to an event which hypothetically might have caused death if it were more severe.

Any new SAE that occurs after the study period should be recorded and reported immediately (cross reference to the Pharmacovigilance section). The study period for the purpose of SAE reporting is defined as the period from the subject's signature on the informed consent form until the end of the follow-up period (30 days following last dose).

SAE Reporting

In order to satisfy regulatory requirements, any SAE, whether deemed IMP-related or not, must be reported to the contract research organization (CRO) as soon as possible after the investigator or coordinator has become aware of its occurrence. The SAE form completion and reporting must not be delayed even if all of the information is not available at the time of the initial contact.

The SAE should be submitted within 24 hours of becoming aware of the event to the CRO. The CRO will forward the report to the appropriate Pharmacovigilance unit at Teva or Local Safety Officer who will forward the SAE report to the Global Pharmacovigilance Unit:

SAEs originating in Europe and rest of the world should be sent to:

Global Drug Safety and Pharmacovigilance Unit (Israel)
[REDACTED]

SAE originated in USA will be sent to:

Teva USA clinical safety mailbox
[REDACTED]

SAE originated in Canada will be sent to:

Teva Canada safety mailbox
[REDACTED]

SAEs originating in Germany will be sent to:

Teva Germany safety mailbox
[REDACTED]

Only in the event of difficulty transmitting the form via email send the form to fax, or contact the sponsor's study personnel identified above for further instruction.

Additional information (follow-up) about any SAE unavailable at the initial reporting should be forwarded by the site within 24 hours of the information becoming available to the contract research organization.

For both initial and follow-up SAE reports the contract research organization forwards this information to the appropriate Pharmacovigilance unit at Teva or Local Safety Officer who forwards it to the appropriate Pharmacovigilance unit at Teva within 48 hours. The Pharmacovigilance units at Teva will submit a summary of the clinical course of the SAEs back to the contract research organization / Local Safety Officer for local submission to the regulatory authorities (competent authorities [CA] and Ethics Committee (EC)/Institutional Review Board (IRB) and investigators according to regulations.

The following information should be provided to accurately and completely record the event:

1. Investigator name and site number
2. Subject number
3. Clinical event:
 - a. description
 - b. date of onset
 - c. severity
 - d. treatment (including hospitalization)
 - e. relationship to IMP (causality)
 - f. action taken regarding IMP
4. If the AE was fatal:

- a. cause of death (whether or not the death was related to the IMP)
- b. autopsy findings (if available)
5. Medical History (copy)
6. Concomitant Medication (copy)
7. Any relevant reports (laboratory, discharge, x-Ray, etc)

This information should be sent to the LCM/ Local Safety Officer who will forward the information to the appropriate Pharmacovigilance Centre at Teva.

In the EU the procedures for notification of suspected unexpected serious adverse reactions (SUSARs) shall be carried out in accordance with EU Directives. SAEs should be reported by the sponsor to EC/IRB according to local requirements.

In non-EU countries, SAEs should be reported by the site to their local EC/IRB as dictated by their board's policies and procedures.

Subjects who have had an SAE during the treatment period must be followed clinically until all parameters (including laboratory) have either returned to normal or have stabilized or are otherwise explained.

Pregnancy reports: Pregnancies should be reported throughout the study. This includes also normal pregnancies without AE. The pregnancy should be followed up to determine outcome, including spontaneous or elective termination, details of birth, and presence or absence of any birth defect, congenital abnormalities or maternal and newborn complications. The pregnancies reporting procedure should be the same as the SAE reporting procedure.

Pregnancy follow-up should be recorded on a specific CRF provided by CRO.

10.1. Protocol-Defined Adverse Events for Expedited Reporting

Ischemic cardiac events (such as myocardial infarction, unstable angina, acute coronary syndrome etc), and cerebrovascular events (such as cerebral arterial occlusion, cerebral ischemia, etc) should be reported to the sponsor within 48 hours, including completion of the corresponding dedicated CRF.

11. STATISTICAL METHODOLOGY

A total of up to 264 subjects, randomized to treatment with 0.3 mg or 0.6 mg of laquinimod, are expected to be recruited into this double-blind, multi-national trial. The trial is planned for 36 weeks of double-blind treatment.

All data summaries in this trial will be presented by treatment group.

The statistical analyses of this study will be exploratory in nature. Continuous variables will be presented by descriptive statistics (mean, standard deviation, minimum, median and maximum values), by treatment group. For categorical variables treatment group counts and percentage from total subject population will be tabulated.

11.1. Sample Size Rationale

Subjects that completed protocol LAQ/5062 will be eligible for inclusion in this trial. LAQ/5062 subjects have no obligation to enter this study, therefore the number of subjects in this study is not determined, but is expected to be less than 264 subjects.

11.2. Randomization Procedure

The randomization scheme for this trial is based on the randomization scheme of protocol LAQ/5062, where each subject was allocated to one of the 3 treatment groups: Laquinimod 0.6 mg, Laquinimod 0.3 mg or placebo.

In this trial the subjects allocated to Laquinimod 0.6 mg and Laquinimod 0.3 mg groups will continue to receive the same treatment, while the subjects allocated to the placebo group will be randomized to receive either Laquinimod 0.6 mg or Laquinimod 0.3 mg.

The randomization scheme for LAQ/5062 placebo group, employing a 1:1 treatment assignment ratio, using blocks stratified by centers, will be prepared by Teva Global BioStatistics and Global BioMedical Informatics units. The scheme will be generated using SAS[®] PLAN procedure. The randomization list and the seed used to generate it will be kept sealed in a fire-protected safe.

This randomization process generates a new 2:2:1:1 treatment assignment ratio, where the assignments are:

- Subjects who were treated by Laquinimod 0.6 mg in both LAQ/5062 and LAQ/5063 studies.
- Subjects who were treated by Laquinimod 0.3 mg in both LAQ/5062 and LAQ/5063 studies.
- Subjects who were treated by placebo in study LAQ/5062 and by Laquinimod 0.6 mg in study LAQ/5063.

- Subjects who were treated by placebo in study LAQ/5062 and by Laquinimod 0.3 mg in study LAQ/5063.

Because there is no obligation of LAQ/5062 subjects to enter this study, there is no guaranty that the 2:2:1:1 randomization scheme will be kept.

In the open-label phase, all subjects will receive laquinimod 0.6 mg daily

11.3. Subjects Cohorts

A single data cohort is defined for this clinical trial. This cohort is:

ITT: Consists of all subjects who have been randomized to the study and received at least one dose of IMP. In accordance with the ITT principle, all subjects randomized will be kept in their originally assigned treatment group.

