7.3.3. Termination Visit

Termination Visit (6) / (Week 36 ± 3 days) of LAQ/5063 Active Double-Blind Phase (Completion of the full 36 weeks or as requested by the sponsor), or any Termination or Early Discontinuation visit occurring as long as the Sponsor continues the development of laquinimod 0.6 mg for RRMS.

In the event of early discontinuation, standard termination procedures will be followed.

Early discontinuation is defined as withdrawal from the study prior to the completion of the full study period:

- Withdrawal prior to completion of 24 months of the first period of open label phase.
- Subjects that chose to continue to the second period of open label phase (additional 36 months), and did not complete this period.
- Subjects that chose to continue treatment from Month 60 as long as the Sponsor continues the development of laquinimod 0.6 mg for RRMS and did not complete this period.

Subjects who are discontinued from study treatment will be encouraged to continue all scheduled visits and procedures until completion of the study (with the exception of procedures associated with drug dispensing and accountability, pregnancy testing, and GFR estimation [including body weight measurement]).

Subjects who have completed 24 months of open label phase and chose not to continue to further extension of open label phase will be regarded as completers.

Subjects who have completed 60 months of the extension open label phase and chose not to continue to further extension of open label phase (as long as the Sponsor continues the development of laquinimod 0.6 mg for RRMS) will be regarded as completers.

The reason for discontinuation of therapy will be documented in the source documents and captured on the CRF. If there are several reasons for early discontinuation, the more severe will be chosen as the primary reason. In the event that laquinimod is discontinued early, an early termination visit should be completed as close to the last dosing date as possible.

Subjects who did not complete the 36 weeks of treatment of LAQ/5063 active double-blind phase until approval of amendment No 2 will be called for an a termination visit of the active double-blind phase as requested by the Sponsor to be switched to the open-label phase (LAQ/5063 OL)

In case a subject completed the 60 months OL period, but decided not to proceed with the further extension, he/she will be considered as completer.

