8.3. Assessment of Subject Compliance

At each study visit, the Investigator, Site Coordinator and/or pharmacist will assess the subject's compliance with the study requirements. This will include checks of protocol compliance and use of laquinimod.

The subject will return all unused tablets and/or capsules (following the switch to capsules) in their original packages, blisters/bottles and all used partially empty and empty blisters/bottles and unused IMP at each visit to the study. Compliance with the dosing regimen will be determined by performing IMP accountability of returned blisters/bottles of the IMP used and unused. The number of unused tablets/capsules will be recorded on the CRF by site personnel. Percent compliance will be calculated as the number of used tablets/capsules divided by the number of total tablets/capsules expected to be used, multiplied by 100.

Subjects with less than 75% overall compliance during the entire study will be considered non-compliant, although they will continue to be followed-up and included in the intent-to-treat (ITT) cohort. Subjects who fail to comply with the study requirements may be withdrawn from the study, following consultation with the Sponsor.

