9.3. Investigational Medicinal Product Manufacturing

Siegfried Ltd., is the manufacturer of laquinimod tablets. Manufacturing was carried out in accordance with GMP applicable to IMPs.

The new study drug, laquinimod capsules 0.6 mg, which will be introduced during the open label phase of LAQ/5063 OL upon approval of Amendment # 4, is manufactured in compliance with current GMP standards by Teva Pharmaceutical Industries Ltd. Israel.

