11.5.5. Drug Tolerability & Drop-Out Assessment

The number and percentage of subjects who failed to complete the study will be presented by treatment groups.

The number and percentage of subjects who prematurely discontinued from the study due to AEs will be presented by treatment groups.

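### Section 11 has no workable rule for grouping and summarising open-label data, and its event summaries carry no person-time

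*Combined protocol and SAP*

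**What the plan says.** Section 11.3 defines a single cohort for the clinical trial: all subjects randomised who took at least one dose. Its grouping rule is "In accordance with the ITT principle, all subjects randomized will be kept in their originally assigned treatment group". The preamble to Section 11 presents every summary by treatment group and describes a trial of 36 weeks of double-blind treatment. Section 11.2 adds that everyone receives 0.6 mg in the open-label phase.

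The summaries most affected are these:

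- **Drop-out (11.5.5):** "The number and percentage of subjects who failed to complete the study will be presented by treatment groups". Section 7.3.3 spells out early discontinuation in three cases, each an open-label period. The first is "Withdrawal prior to completion of 24 months of the first period of open label phase". It counts as completers "Subjects who have completed 24 months of open label phase and chose not to continue to further extension of open label phase", and likewise those who stop after Month 60.
- **Adverse events (11.5.1):** incidence and frequency by treatment group.
- **Relapses (11.4.6, 11.4.7):** the total number, and the count and percentage relapse-free over a treatment period whose phase is not named. Section 4.1.3 lists a relapse rate, but 11.4 specifies none.
- **Laboratory, ECG and vital signs (11.5.2 to 11.5.4):** changes and shifts from the LAQ/5062 and LAQ/5063 baselines. Open-label Month 0 is not named.

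Outside Section 11, 7.3.1.2 and 9.2 say that treatment assignment is relevant to the double-blind phase only. Section 7.3.1.1 says that the IVRS is not used in the open-label phase because all subjects are then in one treatment group.

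**The concern.** Section 4 makes the long-term safety and tolerability of once-daily 0.6 mg the purpose of the open-label phase. Section 3.3.2 records that the data monitoring committee of two other laquinimod studies felt long-term monitoring at this dose was necessary, and that the sponsor is watching cardiovascular events in this study too. The summary tables should therefore show plainly what happened on open-label 0.6 mg.

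An original-assignment rule cannot do that, because after the switch the assigned dose no longer describes the dose taken. If the rule is applied throughout, the 0.6 mg column loses the open-label experience of subjects assigned 0.3 mg, and the 0.3 mg column fills with 0.6 mg exposure. If it is not applied, nothing in Section 11 says what replaces it. Crude percentages add a second difficulty: they are hard to interpret when follow-up runs from months to years.

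**Working it through.** The plan has no power or event calculation to reproduce. Its one derivable figure is the 2:2:1:1 ratio in 11.2. Equal core arms (implied, not stated) with placebo split 1:1 give 1 : 1 : 0.5 : 0.5 = 2:2:1:1, which agrees.

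**Step 1. Does Section 11 reach the open-label phase?**

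*For:*
- The protocol title includes the open-label phase, and 11.3 speaks of the clinical trial without a phase limit.
- Drop-out under 11.5.5, if it uses the 7.3.3 definition, needs open-label data.
- Section 8.3 judges compliance over both phases and keeps poor compliers in the analysis: "although they will continue to be followed-up and included in the intent-to-treat (ITT) cohort". That compliance calculation counts capsules, and 9.3 describes "The new study drug, laquinimod capsules 0.6 mg, which will be introduced during the open label phase of LAQ/5063 OL". This shows that the cohort spans both phases. It does not say how open-label events are grouped.

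*Against:*
- The Section 11 preamble describes 36 weeks of double-blind treatment.
- The MRI summaries in 11.4.1 to 11.4.5 are fixed at Week 36, so open-label scans do not enter them.
- Sections 7.3.1.1, 7.3.1.2 and 9.2 tie assignment to the double-blind phase.

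The text supports two readings and does not choose between them.

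**Step 2. Size on the literal reading only.** Section 7.1 sets a month at 30 days. Double-blind days: 36 × 7 = 252. Open-label days: 24 × 30 = 720 and 60 × 30 = 1800. For a subject assigned 0.3 mg, the share of LAQ/5063 treatment days on 0.6 mg is open-label days / (double-blind days + open-label days).

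| Double-blind length | By open-label Month 24 | By open-label Month 60 |
|---|---|---|
| 36 weeks (252 days) | 720/972 = 74% | 1800/2052 = 88% |
| 24 weeks (168 days), assumed | 720/888 = 81% | 1800/1968 = 91% |
| 12 weeks (84 days), assumed | 720/804 = 90% | 1800/1884 = 96% |

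The shorter rows are shown because 7.3.3 calls in early "Subjects who did not complete the 36 weeks of treatment of LAQ/5063 active double-blind phase until approval of amendment No 2"; how early is not stated. At the ceiling of 264 subjects and 2:2:1:1, subjects assigned 0.3 mg number 264 × (2 + 1)/6 = 132, or half. Sections 11.1 and 11.2 guarantee neither figure.

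**Step 3. Unequal follow-up.** Section 7.1 leaves the open-label phase running for as long as development continues. Two completers under 7.3.3 can have 720 and 1800 open-label days, a ratio of 1800/720 = 2.5. To show what this does to a crude percentage, assume one constant event rate and compute 1 − exp(−rate × days/365.25):

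| Assumed rate per patient-year | 252 days | 972 days | 2052 days |
|---|---|---|---|
| 0.05 | 3.4% | 12.5% | 24.5% |
| 0.10 | 6.7% | 23.4% | 43.0% |
| 0.20 | 12.9% | 41.3% | 67.5% |

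The underlying rate is the same along each row; only follow-up differs. The rates are illustrative, not taken from the documents.

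**The case against.** The strongest reply is that Section 11 was written for the double-blind phase and is sound within it. Sections 7.3.1.2 and 9.2 limit assignment to that phase, and 7.3.1.1 places all open-label subjects in one treatment group. Section 11.2 says that in this trial subjects on 0.3 mg keep the same treatment, which is untrue of the open-label phase. The open-label sentence in 11.2 came with Amendment 9 as a clarification (Section 21.2). The missing Month 0 baseline points the same way. Figure 1, whose title covers treatment groups in both phases, is not visible here, and Appendix 4 mentions an analytical plan for MSFC scoring that is not among these documents.

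Much of this stands. A reader might infer that the plan will report open-label 0.6 mg data under 0.3 mg. The documents never say so; it is the literal consequence of 11.3 and not the only reading. A reader might also take 74% and 88% as shares of misplaced events. They are shares of days. Sections 3.4.1.1, 3.4.1.4 and 3.4.1.6.1 describe reactions that mostly arise early in treatment, so event shares could differ considerably.

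The reply does not remove the gap. Section 11.3 does not refer to the operational sections, 11.5.5 has no double-blind definition of completion, and 18.4.2 says that the analysis is performed as the protocol defines it. If the narrower reading is right, the open-label objective in Section 4 has no written analysis.

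**Conclusion.** The point holds in this form: Section 11 does not give a workable rule for open-label data. One reading files open-label 0.6 mg experience under 0.3 mg; the other leaves the long-term 0.6 mg objective without a stated analysis. On either reading the adverse-event, relapse and drop-out summaries specify no person-time.

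The 74% and 88% rest on the literal reading, a full 36-week double-blind phase, 30-day months and continuous treatment to the month named. The consequence is confined to summary tables. The analyses are exploratory and descriptive, so no test result changes. Serious adverse events are still discussed case by case (11.5.1), and ischaemic cardiac and cerebrovascular events have expedited reporting (10.1). The point does not touch the Week 36 MRI summaries. Nor does it require the double-blind tables to be recast by the four sequences, which 11.2 already lists. It is worth fixing because the remedy is cheap and serves a stated objective.

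**What to change.** 1. In 11.3, limit the original-assignment rule to the double-blind phase.
2. Define an open-label set of subjects with at least one open-label dose. Tabulate their safety, relapse and drop-out data as 0.6 mg received, with open-label Month 0 as an added baseline. Show rates per 100 patient-years beside the counts and percentages, optionally split by prior treatment sequence and by time period. State where patient-years end, since 7.1 keeps subjects who stop drug on scheduled visits.
3. State whether the summaries in 11.4.6 to 11.4.9 stop at double-blind termination. This matters for the EDSS change in 11.4.9, which uses the last recorded score with no phase limit.

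**Cost:** wording in Section 11 and more tables; no new data or subjects. A single rate per patient-year assumes a constant hazard and can dilute reactions that occur early, so the crude figures should stay or the rates should be split by period. A single 0.6 mg open-label column drops the view by original assignment; the optional split by prior sequence keeps it.
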